## 1. AMENDMENT HISTORY

Amendment No.	Protocol Version No.	Date issued	Author(s) of changes	Details of Changes made
	0.1	29/6/18	[name] [name] [name] [name] [name]	Revision of the protocol pre-sponsor submission.
	0.2	8/8/18	[name]	Pre-sponsor submission
	0.3	22/8/18	[name]	Post-sponsor review revisions
	1	30/8/18	[name]	Post-sponsor review
	2	30/10/18	[name]	Post-Rec review
	3	14/11/2018	[name]	Substantial amendment: 

1. Change to order of study assessments

2. Participants will be asked to take dietary and lifestyle measures prior to assessment

3. Participants will not be withdrawn for low compliance

4. Participants cannot use tablet devices

	5	21/2/19	[name]	Substantial amendment: 

1. Addition of a post-stroke sub-group

2. Provision of laptops to participants where necessary

				
 
3. To interview the healthy participant sub-group
 
4. To remove the upper limit on the MoCA cut-off
 

	6	5/9/19	[name]	
Substantial amendment:
 
To increase the number of cognitive tasks for the post-stroke sub-group
 
To collect data on the type, location, and size of the infarct

	7	19/12/19	[name]	Removal of age limit on stroke sub-group (50 years)

List details of all protocol amendments here whenever a new version of the protocol is produced.

## 2. SYNOPSIS

Study Title	The Cognition and Flow Study: The Effects of Brain Training on Brain Blood Flow
Internal ref. no.	0677
Trial Design	Feasibility Randomised Controlled Trial
Trial Participants	Healthy older adults, adults with mild cognitive impairment (undifferentiated), adults with mild to moderate Alzheimer's disease, adults 12 months post-ischaemic stroke.
Planned Sample Size	80 participants in total, 20 participants in each of the four sub-groups.
Follow-up duration	Three to six months
Planned Trial Period	12 -18 months
Primary Objective	The primary objective of this study is to determine the ability to carry out (feasibility) of a large scale randomised controlled trial (RCT) of cognitive training (CT) in healthy older adults (HC), and people with Alzheimer's disease (AzD), mild cognitive impairment (MCI), and people post-ischaemic stroke.
Secondary Objectives	Are there any clinical benefits of a CT program in patients with dementia and any difference between groups (MCI/AzD/healthy older adults/post-ischaemic stroke) in ability to carry out everyday activities, memory, mood, and quality of life outcomes?
Primary Endpoints	
 
1) Percentage of participants successfully recruited
 
2) Percentage of participants able to successfully complete CT program and complete all assessments
 
3) Percentage of participants with full bilateral data for CBFv
 
4) Feasibility of randomisation to waiting list control
 

Secondary Endpoints	
 
1) Change in cognition score as detected by the Addenbrooke's cognitive examination (ACE-III)
 
2) Change in functional status - Lawton Instrumental Activities of Daily Living (IADL)
 

	
3) Change in mood – Geriatric Depression Scale (GDS-15)
 
4) Change in quality of life measure – Dementia Quality of Life Measure (DEMQOL)
 
5) Change in task activation increase in CBFv from baseline

Qualitative objectives	
The third element to this study is a qualitative component which will seek to explore any patient or carer benefits or harms not identified by the traditional measures listed above, specifically:
 

• What are the barriers to CT in patients with dementia?

• What are the facilitators (benefits) to brain training in patients with dementia?

• Could CT programs be adapted further to support the participation of patients with dementia?

• Are there any additional benefits to CT programs not measured by traditional methods as perceived by the patients and their carers?

• To explore the lived experience of the patient and their carer and the impact CT has on them and their life

### 3. ABBREVIATIONS

AE	Adverse event
ACE-III	Addenbrooke's Cognitive Examination III
ADL	Activities of Daily Living
ANOVA	Analysis of Variance
AR	Adverse reaction
AzD	Alzheimer's disease
CBFv	Cerebral blood flow velocity
CHIASM	Cerebral Haemodynamics in Ageing and Stroke Medicine
CI	Chief Investigator
CRA	Clinical Research Associate (Monitor)
CRF	Case Report Form
CRN	Clinical Research Network
CRO	Contract Research Organisation
CT	Cognitive Training
DEMQOL	Dementia Quality of Life Measure
EC	Ethics Committee (see REC)
ETCO 2	End-tidal CO 2
GCP	Good Clinical Practice
GDS	Geriatric Depression Scale
GP	General Practitioner
GTAC	Gene Therapy Advisory Committee
HC	Healthy control
HR	Heart Rate
IADL	Instrumental Activity of Daily Living
ICF	Informed Consent Form
MAP	Mean Arterial Pressure
MCA	Middle Cerebral Artery
MCI	Mild cognitive impairment
NHS	National Health Service
NRES	National Research Ethics Service
PI	Principal Investigator
PIL/S	Participant/ Patient Information Leaflet/Sheet
QoL	Quality of Life
RCT	Randomised controlled trial
R&D	NHS Trust R&D Department
REC	Research Ethics Committee
SAE	Serious Adverse Event
SAR	Serious Adverse Reaction
SOP	Standard Operating Procedure
SUSAR	Suspected Unexpected Serious Adverse Reactions
TCD	Transcranial Doppler ultrasonography

TMF	Trial Master File
TSC	Trial Steering Committee

#### 4. BACKGROUND AND RATIONALE

##### **Disease Characteristics and Population Studied**

The incidence of dementia is rising as the population ages, with 850,000 patients currently living in the UK alone (1). By 2026, this is projected to have risen by a further 40% (1). However, there are currently few diagnostic or therapeutic strategies available to offer patients. Dementia is a progressive condition characterised by gradual loss of cognitive or non-cognitive higher functions (i.e. language, visuospatial, attention) (2). Dementia is an umbrella term that encompasses a number of cognitive disorders including; Alzheimer's disease (AzD), vascular dementia, Lewy body dementia, fronto-temporal dementia and Parkinson's dementia (2). Mild cognitive impairment (MCI) is characterised by subjective and objective decline in cognitive function, but with preserved functional independence in daily living (3). It has become increasingly recognised that deranged vascular function is an early contributor to the deposition of amyloid plaques and tau tangles in AzD, and that these pathologies exacerbate one another (two-hit hypothesis) (4). In a recent systematic review and meta-analysis undertaken by this group, we demonstrated clear abnormalities in vascular function across a number of imaging modalities at the MCI stage (5). Thus, treatments that can improve cerebral perfusion or vascular function could represent an early treatment option for dementia (5). In this study, the target populations are; healthy older adults (as controls), adults with AzD, and MCI, to capture the effects of brain training (BT) on vascular physiology at an early stage in the dementia process.

##### **Summary of the Project and Evidence Base**

This project is a feasibility randomised controlled trial (RCT) as part of a PhD qualification to examine the use of a brain training (BT) program in adults with MCI, early AzD and healthy older adults (HC). In addition to measuring cognitive and functional outcomes, this study will also use transcranial Doppler ultrasonography (TCD) to measure changes in cerebral blood flow before and after an 8-12-week CT program. A recent systematic review found that longer, more intensive programs appeared to have no benefit over shorter programs, which are more likely to encourage adherence for patients with cognitive impairment (6, 7).

The evidence for CT in MCI, AzD, and vascular dementia (VaD) is heterogeneous, and frequently of low quality (8, 9). Few studies have included neuroimaging outcomes to explore brain plasticity or neural mechanisms underlying changes in cognition after CT (10). Therefore, this study not only addresses the development of a future high quality RCT of CT

in dementia, but also aims to fill the evidence gap on the use of TCD to assess neurovascular plasticity.

The use of TCD is a novel method to investigate for neurovascular training effects and for markers predictive of which patients may benefit from particular CT programs. This would allow the development of a personalised approach to developing CT programs for people with dementia. Given its low cost, portability and acceptability (11, 12), further studies are required to investigate the utility of TCD in older people and those living with dementia.

CT provides an attractive treatment target in dementia given there are few side effects and it is relatively cheap (7). However the evidence base at present is unclear, largely due to the poor quality studies that have been carried out to date (8, 9). Therefore, this study provides the basis for designing a high quality RCT of CT in dementia that can help address this issue.

Furthermore, this study will include a qualitative component to explore any benefits, problems or barriers to engaging with the training program that could be improved upon in future studies, and identify any benefits not measured by traditional outcomes.

### TCD

TCD is a non-invasive, ultrasound based imaging modality that allows measurements of cerebral blood flow velocity (CBFv) at rest (13) and following activation by cognitive tasks (14). TCD has a number of advantages over other functional imaging techniques (magnetic resonance imaging (MRI) and positron emission tomography (PET)), including lower cost, portability, relative ease of operator training, and higher acceptability to patients (12, 15). TCD is particularly suited to older people, and those with dementia, as it can be used in patients with pacemakers, metal implants and claustrophobia (12).

### Cognitive Training

Cognitive interventions can be considered as three broad categories; CT, cognitive rehabilitation and cognitive stimulation (9, 16). CT describes a structured, guided program of standardised tasks designed to provide practice or training with a specified cognitive domain(s), to translate into functional benefits (9, 16). This is distinguished from cognitive rehabilitation, where patient centered approaches and goals are used to improve everyday function, rather than improve cognition function (8, 9, 16), and cognitive stimulation which aims to generally improve cognition, social function and quality of life (17). CT is attractive in that it offers a cost effective, non-invasive and acceptable intervention to patients, with no reported adverse effects (18). A recent systematic review of 51 RCTs demonstrated improvements with CT in overall cognition, non-verbal memory, working memory, processing

speed, and visuospatial skills in healthy older adults (6). High quality RCT evidence is however lacking in studies of CT in dementia (7-9, 19). Two previous Cochrane reviews (8, 9), demonstrated the evidence was sparse, with many of the studies under-powered, of low-to-moderate quality, and with relatively few for MCI (8, 9). Recent systematic reviews of CT in MCI have demonstrated moderate benefits in verbal learning and memory, global cognition, non-verbal learning, working memory, attention and psychosocial functioning (19, 20). Thus far, studies of CT in dementia have been heterogeneous in study design, participants included, type and definition of training, outcome measures, and duration and intensity of intervention (7-9, 21, 22). This hampers the adequate meta-analysis of data and of conclusions that can be drawn from pooled analyses (7, 10).

### Neuroimaging and CT

The use of neuroimaging outcomes has also been limited in CT studies (10, 23), but understanding the training effects occurring at the physiological level would provide important mechanistic information to any potential benefits conferred by CT (24-26). Belleville et al demonstrate increased parietal activation in patients with MCI, following a multi-modal CT program designed to improve episodic memory (24). In a near-infrared spectroscopy study by Vermeij et al, patients with MCI had greater training benefits at high load working memory where participants had greater pre-frontal activation (27), and baseline global and hippocampal atrophy were predictive of poorer training gains in healthy older adults and those with MCI (25). Therefore, imaging biomarkers can potentially be used to predict and tailor interventions to individual patient's needs (25, 26). Whilst a number of studies have demonstrated positive structural and functional effects of CT (26, 28, 29), they have largely focused on healthy older adults (28), the use of structural (28) or functional MRI (24, 25), and PET (30, 31), but there have been no TCD studies examining changes in neurovascular response to CT in patients with cognitive impairment.

**5. OBJECTIVES**

### 5.1 Primary Objectives

The primary objective of this study is to determine the ability to carry out (feasibility) a large scale RCT of CT in healthy older adults, and people with AzD and MCI.

### 5.2 Secondary Objectives

- 1) Are there any clinical benefits of a brain training program in patients with dementia and any difference between groups (MCI/AzD/healthy older adults/post-ischaemic stroke) in ability to carry out everyday activities, memory, mood, and quality of life outcomes?
- 2) Are there any changes in blood flow responses to cognitive tasks using TCD before and after brain training?
- 3) Are there any brain blood flow markers that can be used to predict who will benefit from brain training, and in which memory areas to generate a personalised training plan for individual patients?

### 5.3 Qualitative Study Objectives

- 1) What are the barriers to brain training in patients with dementia?
- 2) What are the facilitators (benefits) to brain training in patients with dementia?
- 3) Could brain training programs be adapted further to support the participation of patients with dementia?
- 4) Are there any additional benefits to brain training programs not measured by traditional methods as perceived by the patients and their carers?
- 5) To explore the lived experience of the patient and their carer and the impact brain training has on them and their life.

## 6. STUDY DESIGN

### 6.1 Summary of Trial Design

This is a prospective, feasibility, RCT of CT in healthy older adults, and adults with AzD, MCI, or post-ischaemic stroke. This trial is un-blinded, due to the nature of the intervention. The expected duration of participation per individual is three to six months. Initially, participants will be approached by a member of the clinical care team or research support staff, who will screen and identify eligible participants. Study specific information will then be provided by the researcher. Following this, participants will undergo informed consent. Each participant will have two visits (initial and follow-up assessment). After the first visit, participants will be randomised to control or intervention (CT), and will complete an 8-12 week CT program, if selected for the intervention group. Participants will be randomised using Sealed Envelope ©, an online, commercially available randomisation tool. At the end of the trial, participants will be given the option to participate in a qualitative study by semi-structured interviews or focus group. A flow chart for this process can be seen in Appendix A.

## 6.2 Primary and Secondary Endpoints/Outcome Measures

Primary end point measures:

- 1) Number of participants successfully recruited
- 2) Percentage of participants able to successfully complete the CT program and all assessments
- 3) Percentage of participants with full bilateral data for CBFv
- 4) Feasibility of randomisation to waiting list control

Secondary end points:

- 1) Change in cognition score as detected by the Addenbrooke's cognitive examination (ACE-III)
- 2) Change in functional status - Lawton IADL
- 3) Change in mood – GDS-15
- 4) Change in quality of life measure – DEMQOL
- 5) Change in task activation increase in CBFv from baseline

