#### Feasibility and Baseline Demographics

Data will be reported as mean (standard deviation) for continuous variables, and number (percentage) for nominal data. Differences between the intervention and control groups will be analysed within population group (HC/AzD/MCI) using Chi-Square for nominal data, and independent t-testing for continuous data. Any differences between population groups will also be reported.

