#### **Waiting list control for intervention**

All study participants who are randomised to the control arm will be offered the intervention at the end of the study (waiting list control). This is not a cross over trial, and therefore these participants will not have any further assessments after provision of the CT program. This is to remove any ethical concerns about participants not being able to undertake the CT program through study participation. Some participants may deteriorate over the course of the study and may be unable to utilise the intervention effectively as waiting list control.

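### Primary endpoint 2 is a single joint percentage for training and assessments, so it cannot describe retention in the control arm or separate non-adherence from loss to follow-up in the training arm

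*Combined protocol and SAP*

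**What the plan says.** Section 6.2 lists four primary endpoints. The second is "Percentage of participants able to successfully complete the CT program and all assessments". The synopsis words it as "Percentage of participants able to successfully complete CT program and complete all assessments". Both make it one joint criterion. Neither gives a denominator, an arm, or a definition of successful completion.

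Section 6.1 gives every participant a baseline and a follow-up visit, but a participant "will complete an 8-12 week CT program, if selected for the intervention group". Section 14.1 (Waiting list control for intervention) offers controls the programme at the end of the study and adds that "these participants will not have any further assessments after provision of the CT program".

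Three other parts of the plan bear on the point:

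- **Other primary endpoints (6.2).** Endpoint 1 is recruitment. Endpoint 3 is "Percentage of participants with full bilateral data for CBFv", with no arm or visit named. Endpoint 4 is "Feasibility of randomisation to waiting list control", with no metric.
- **Arm comparisons (11.1, Feasibility and Baseline Demographics).** "Differences between the intervention and control groups will be analysed within population group (HC/AzD/MCI) using Chi-Square for nominal data". No retention or follow-up variable is named.
- **Data recorded.** Section 9.3 logs training time and keeps non-adherent participants in the study, because adherence is part of the feasibility question. Section 8.9 records the reason for withdrawal on the CRF.

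**The concern.** Training adherence and attendance at follow-up are different feasibility parameters, and they lead to different decisions about a large trial. Poor adherence points to changing the programme or its support. Poor attendance points to changing the follow-up or enlarging the sample. A joint percentage gives one number for both.

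The waiting-list design adds a second difficulty. Controls have no programme to complete before their follow-up visit, so a criterion that requires programme completion cannot say whether controls came back. Section 5.1 makes the feasibility of a large RCT the primary objective, and section 11.1 (Power calculation) says the results will inform the sample size of a larger trial. That calculation needs retention, preferably by arm, because loss may differ between people who train five times a week with weekly calls and people who wait.

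**Working it through.** The documents give no completion rate, retention rate or target, so there is no plan figure to reproduce. The check compares the definition with the design and then illustrates the consequences with assumed rates.

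**Inputs from the documents.** Planned size is 80 (synopsis, 4 × 20) or 60 (sections 11.2 and 14.1, 3 × 20). Section 8.5 specifies permuted blocks without a ratio.

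**Assumptions.** 1:1 allocation, giving 40 or 30 per arm; programme completion counted up to the follow-up visit; the rates below.

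**Step 1: all randomised as denominator.** Controls contribute zero to the numerator whether or not they attend.

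- Ceiling: 40/80 = 50%, or 30/60 = 50%.
- If 70% of trainees meet the joint criterion: 28/80 = 35%, or 21/60 = 35%.

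**Step 2: training arm only as denominator.** There is no structural zero, but controls are absent and the two components are still merged. Joint percentage = retention × programme completion among those retained. A reported 70% fits each of these rows:

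| Retention | Completion among retained | Product |
|---|---|---|
| 70% | 100% | 70% |
| 80% | 87.5% | 70% |
| 90% | 77.8% | 70% |
| 100% | 70% | 70% |

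**Step 3: consequence for a later trial.** Number to randomise per arm = evaluable number / retention. Taking 100 evaluable per arm as an example:

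- 100/0.70 = 143
- 100/0.80 = 125
- 100/0.90 = 112
- 100/1.00 = 100

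Reading the joint 70% as retention gives 143 in all four cases. Reading the diluted 35% from step 1 as retention would give 100/0.35 = 286.

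**Step 4: whether another primary endpoint supplies retention by arm.** Endpoint 1 concerns entry to the study. Endpoint 3 depends partly on attendance if it covers both visits, but it also depends on signal quality and is not stated by arm or visit. Endpoint 4 concerns the control arm but has no measure. The comparison in 11.1 names no retention variable, and if it were applied to endpoint 2 it would set a rate against a structural zero.

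**Step 5: precision if retention is reported by arm.** Exact (Clopper-Pearson) 95% intervals for an observed 80%:

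- 32/40: 64% to 91%
- 24/30: 61% to 92%
- 8/10 (about one arm within one population group): 44% to 97%

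For the arm difference, 38/40 against 32/40 is 95% − 80% = 15 points, with a Newcombe 95% CI of 0.1 to 30.2 points. The pooled figures by arm are usable for planning. Those within a population group are not.

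**The case against.** The ordinary reading of endpoint 2 is that it concerns the training arm, since only that arm has a programme during the assessed period. On that reading no control is scored as a failure. A joint percentage of participants both trained and fully assessed is also a legitimate feasibility summary. The components are not lost: training time is logged, withdrawal reasons go on the CRF, missing data are to be reported (11.5), and both arms have a follow-up visit. Endpoint 4 may be where control retention was meant to sit, and 11.1 shows that comparing arms on feasibility data is intended.

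Much of this stands, and it rules out several stronger readings:

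- A reader might infer that endpoint 2 is capped at 50%. That needs an all-randomised denominator and 1:1 allocation. Section 11.7 includes all randomised in the analysis but is not tied to this endpoint, and no ratio is stated.
- A reader might infer that no primary endpoint could cover control retention. Endpoint 4 is undefined, so the documents neither include retention in it nor exclude it.
- A reader might infer that retention by arm could not be recovered, or that controls' later training goes unrecorded. The first is contradicted by the planned data. On the second, section 14.1 rules out further assessments but does not address software logs.
- A reader might rank differential loss as the chief threat to a later trial. The documents give no such ranking.

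The training-arm reading does not remove the central point. It leaves control retention unreported and still merges adherence with attrition.

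**Conclusion.** The point holds as a gap in endpoint definition, not in data collection. Under either denominator, endpoint 2 gives no information on control retention and does not separate non-adherence from loss to follow-up among trainees. No other primary endpoint is defined so as to supply retention by arm.

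The size depends on assumed rates. A joint 70% in the training arm is compatible with retention from 70% to 100%, which is a range of 143 to 100 randomised per arm for 100 evaluable. The 50% ceiling is conditional as described above. The change is worth making, because otherwise the choice of retention measure would be left until after the data are seen. It does not call into question whether the study can be run.

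**What to change.** In section 6.2 and the synopsis, replace endpoint 2 with two figures:

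- **2a.** Percentage of those randomised to training who complete the programme, taken from the training log, with the sponsor stating what counts as completion.
- **2b.** Percentage of all randomised who complete the follow-up assessments, reported by arm, with the arm difference and its 95% CI.

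Alternatively, define endpoint 4 so that it includes 2b. Keep the joint percentage as a description of the training arm only. Name 2b in section 11.1 under Feasibility and Baseline Demographics, and state the denominators once the planned total (60 or 80) and the allocation ratio are settled.

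The cost is wording in the synopsis, 6.2 and 11.1. No new data, visits or participants are needed. The downside is one more primary feasibility figure, with the modest precision by arm shown above, so it should be reported as an estimate with its interval and not as a test.
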